If discontinuation of investigational treatment occurs, the investigator should make a reasonable effort to understand the primary reason for the subject's premature discontinuation of investigational treatment and record this information. Always consider reasons which are related to safety and efficacy first.

Subjects who discontinue investigational treatment or who decide they do not wish to participate in the study further should NOT be considered withdrawn from the study UNLESS they withdraw their consent (see [Section 9.1.3](#)). They will be expected to perform the Visit 9998/EOT (Week 104) assessments 4 weeks after their last dose and will be expected to perform assessments at follow-up Visit 9999, 12 weeks after Visit 9998/EOT. If they fail to return for these assessments for unknown reasons, every effort (e.g., telephone, e-mail, letter) should be made to contact the subject/pre-designated contact as specified in [Section 9.1.4](#). This contact should preferably be done according to the study visit schedule.

For subjects who wish to prematurely discontinue treatment prior to the primary endpoint for any reason, every effort should be made to have them continue study visits as per the assessment schedule, at least until Visit 204 (Week 12). At the final visit, all dispensed investigational product should be reconciled and the AE and concomitant medications reconciled on the appropriate eCRF.

If the subject cannot or is unwilling to attend any visit(s), the site staff should maintain regular telephone contact with the subject, or with a person pre-designated by the subject. This telephone contact should preferably be done according to the study visit schedule until a decision is made to return to the site for discussion about ongoing treatment, or to discontinue treatment/study.

The investigator must also contact the IRT to register the subject's discontinuation from study treatment.

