9.1.5 Early study termination by the sponsor

The study can be terminated by Novartis at any time. Reasons for early termination may include.

- Unexpected, significant, or unacceptable safety risk to subjects enrolled in the study
- Decision based on recommendations from applicable board(s) after review of safety and efficacy data
- Discontinuation of study drug development

In taking the decision to terminate, Novartis will always consider subject welfare and safety. Should early termination be necessary, subjects must be seen as soon as possible and treated as a subject who discontinued from study treatment. The investigator may be informed of additional procedures to be followed in order to ensure that adequate consideration is given to the protection of the subject's interests. The investigator or sponsor depending on local regulation will be responsible for informing IRBs/IECs of the early termination of the trial.

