
To describe the efficacy of ligelizumab in the treatment of CSU, 12 weeks after starting self-administration	
The proportion of subjects with well-controlled disease ($UAS7 \leq 6$), 12 weeks after starting self-administration
For safety & tolerability evaluation:	

To assess the safety and tolerability of ligelizumab in all subjects	
In each dose group, and for each duration of treatment:
 
Occurrence of treatment emergent adverse events during the studyOccurrence of treatment emergent serious adverse events during the studyVital signsLab assessments

To assess the safety and tolerability of ligelizumab 120 mg q4w 1mL pre-filled syringe (PFS)	
For the duration of treatment:
 
Occurrence of treatment emergent serious adverse events during study Week 12 onwardsVital signs Week 12 onwardsLab assessments Week 12 onwards

To assess the safety and tolerability of ligelizumab 120 mg q4w in all subjects who self-administer	
Occurrence of treatment emergent adverse eventsOccurrence of treatment emergent serious adverse eventsVital signsLab assessments

Objective(s)

Endpoint(s)

On 06 April 2022, following extensive assessment of data from the Phase III studies (CQGE031C2302, CQGE031C2303) of ligelizumab in CSU, Novartis communicated a strategic decision to discontinue further clinical development of ligelizumab in chronic urticaria (CSU and chronic inducible urticaria (CINDU)). The decision to not proceed was not based on

any safety concerns with ligelizumab. As a result of this decision, this study CQGE031C2302E1 was terminated.

2 Statistical methods

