2.1.1.2 Study periods

The following study periods will be considered for analysis:

- Screening period (SCR): from the date of signing informed consent form (ICF) to, and not include the date of the first ligelizumab treatment (i.e. V201) in extension, or the first visit in the first observation period (i.e. V101), whichever comes first.
- First observation period (OBS1): from Visit 101 up to Visit 199. The duration of OBS1 period for each subject varies, as it depends on occurrence of relapse ($UAS7 \geq 16$). Maximum duration of OBS1 is 36 weeks.
- First 12 weeks of the first half of the treatment period (TRT1A): from Visit 201 to Visit 204.
- Week 12 to Week 52 of the first half of the treatment period (TRT1B): from Visit 204 to Visit 214 or 301, whichever comes first.
- Entire first half treatment period (TRT1): from Visit 201 to Visit 214 or 301, whichever comes first.
- Second observation period (OBS2): from Visit 301 up to Visit 399. The duration of OBS2 period for each subject varies, as it depends on occurrence of relapse ($UAS7 \geq 16$). Maximum duration of OBS2 is 52 weeks.
- Second half of the treatment period (TRT2): Visit 214 to Visit 9998 (excluding Visit 301 to Visit 399)
- Follow-up period:
 - Subjects who do not complete a continuous 104-week treatment will enter the follow-up period (FU12) for 12 weeks duration and will only perform Visit 9999.
 - Subjects who have completed the full 104-week treatment period without interruption will enter the follow-up period (FU52) of 52 weeks duration and will perform Visit 501 to Visit 9999 (Week 116 to Week 156).

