2.1.1.3.2 Study week in the treatment period

The *study week in the treatment period* defined in this section will be used for the primary and secondary efficacy analyses based on the eDiary. Other assessments collected on Rave CRF visit will be analyzed according to the CRF collected visit weeks. Note that the “baseline week” (Baseline) is comprised of the 7 days prior to Day 1 (Day -7 to Day -1).

For all subject in SAF, study weeks (Week *x*) in the first half of the treatment period (including 12 week-follow up in case of early discontinuation) are defined based on the study days as indicated in Table 2-1:

Table 2-1 Study Week definition based on Study Day, first half of the treatment period (including 12 week-follow up in case of early discontinuation)

Study Week (x)	Study Days
Baseline	Day (-7) ~ (-1)
Week 1	Day 1 ~ 7
...	...
Week x	Day $[7 \times (x-1) + 1] \sim [7 \times x]$
...	...

Study Week (x)	Study Days
Week 52	Day 358 ~ 364

For subjects who **enter the second half of the treatment period without entering OBS2** (including subjects in the continuous long term treatment subpopulation), study weeks (Week x) in the second half of the treatment period (including 12 week-follow up in case of early discontinuation) are defined based on the study days as indicated in Table 2-2a:

Table 2-2a Study Week definition based on Study Day, second half of the treatment period (including 12 week-follow up in case of early discontinuation), for subjects who enter the second half of the treatment period without entering OBS2

Study Week (x)	Study Days
Week 52	Day 358 ~ 364
...	...
Week x	Day $[7 \times (x-52) + 358] \sim [7 \times (x-51) + 357]$
...	...
Week 104	Day 722 ~ 728

For subjects who **enter the second half of the treatment period after entering OBS2** (i.e. subjects in the long-term treatment with a rest subpopulation), study weeks (Week x) in the second half of the treatment period (including 12 week-follow up in case of early discontinuation) are defined based on the study days and study day of Visit 214 (Day c) as indicated in Table 2-2b:

Table 2-2b Study Week definition based on Study Day, second half of the treatment period (including 12 week-follow up in case of early discontinuation) , for subjects who enter the second half of the treatment period after entering OBS2

Study Week (x)	Study Days
Week 52 (V214)	Day $c \sim 6+c$
...	...
Week x	Day $[7 \times (x-52) + c] \sim [7 \times (x-51) + c - 1]$
...	...

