2.5.3 Handling of missing values/censoring/discontinuations

The UAS7 score is derived from the sum of the HSS7 score and the ISS7 score, as noted above. The HSS7 and ISS7 score will be derived by adding up the daily HSS and ISS scores of the 7 days preceding the visit, respectively. The daily score (HSS and ISS) will be calculated by averaging the morning and evening HSS and ISS score, respectively. If one of the morning or evening scores is missing, the non-missing score for that day (morning or evening) will then be used as the daily score.

A minimum of 4 out of 7 daily scores are needed to reliably calculate a weekly HSS7, ISS7 or UAS7 score. For each weekly score from UPDD (i.e. HSS7, ISS7 and UAS7 score), if one or more of the daily scores are missing, the following principles will be applied to handle the missing data:

- If a subject has at least 4 “non-missing” daily scores within the 7 days prior to the study visit, the weekly score will be calculated as the sum of the available eDiary scores of that week, divided by the number of non-missing days, multiplied by 7.
- If there are less than 4 “non-missing” daily scores within the prior 7 days, then the weekly score will be considered as missing for that week.

Subjects who discontinue from study treatment early will be encouraged to stay in the study following the procedures described in the study protocol Section 9.1.1. These are considered as retrieved dropout (RDO) subjects.

The primary analysis will account for different post-dosing events for missing data handling as follows:

- Discontinuation of initially assigned study treatment prior to Week 12 (Visit 204) due to AEs or lack of efficacy or any other reasons, except for the reason of study early termination: Retrieved dropout (RDO) data collected after study treatment discontinuation will be used for analysis. If no RDO data was collected after study treatment permanent discontinuation, non-responder imputation will be applied for missing data imputation.
- Discontinuation of initially assigned study treatment prior to Week 12 (Visit 204) due to study early termination: the efficacy data collected after the discontinued treatment will be censored. The missing data caused by this intercurrent event occurrence will be imputed based on the treatment arm (ligelizumab 72 mg or 120 mg q4w) data under the missing at random (MAR) assumption using multiple imputation separately.

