2.14.8 Handling of missing values/censoring/discontinuations

The missing data handling and imputation rules as described in Section 2.5.3 and Section 2.6.3 will be applied on the primary and some key secondary endpoints, respectively. All the other analyses in the final analysis will be based on the observed data.

Table 2-16 Overview of final analysis

Population/ Analysis /Study Period	Endpoints
First treatment period (TRT1)	
Analysis: Efficacy Populations: 1) FAS 2) Ligelizumab retreatment subpopulation 3) Ligelizumab responder retreatment subpopulation Period/time point: TRT1/up to week 52	
• Proportion of subjects with well-controlled urticaria ($UAS7 \leq 6$) at Week 12

Analysis: Efficacy
 
Populations:
 
 1) FAS 2) Ligelizumab retreatment subpopulation 
Period/time point: TRT1/up to week 52
	
 • Proportion of subjects with completely controlled disease (UAS7 = 0) at Week 12

Analysis: Efficacy
 
Populations:
 
 1) FAS 2) Ligelizumab retreatment subpopulation 
Period/time point: TRT1/up to week 52
	
 • Absolute and percent change from extension study baseline in the UAS7 and its components (ISS7 and HSS7) at Week 12 • Percentage of subjects achieving DLQI = 0-1 at Week 12

Analysis: Efficacy
 
Populations:
 
 1) FAS 2) Ligelizumab retreatment subpopulation 
Period/time point: TRT1A/up to week 12
	
 • Cumulative number of weeks that subjects achieve weekly angioedema activity score (AAS7) = 0 between extension study baseline and Week 12

Analysis: Efficacy
 
Population: Self-administration subpopulation
 
Period/time point: 12 weeks after starting self-administration in TRT1
	
 • The proportion of subjects with well-controlled disease (UAS7 ≤ 6), 12 weeks after starting self-administration

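### SAP Table 2-1 labels post-stop follow-up diary weeks as treatment weeks, and the rule censoring scores after sponsor termination ends at Week 12, so later efficacy summaries can include off-drug scores

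*SAP*

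**What the plan says.** **Week labels.** SAP 2.1.1.3.2 states that, for all subjects in the safety set, study weeks "in the first half of the treatment period (including 12 week-follow up in case of early discontinuation) are defined based on the study days". The numbering "defined in this section will be used for the primary and secondary efficacy analyses based on the eDiary". No other label fits these data: the follow-up weeks in SAP Table 2-5 count from Visit 501, which subjects in the 12-week follow-up do not perform.

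**Periods.** SAP 2.1.1.2 lists the 12-week follow-up apart from TRT1: "Subjects who do not complete a continuous 104-week treatment will enter the follow-up period (FU12) for 12 weeks duration". TRT1 runs from Visit 201 to Visit 214 or 301.

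**Termination.** SAP 1.2 records the sponsor's decision of 06 April 2022: "As a result of this decision, this study CQGE031C2302E1 was terminated". Under Protocol 9.1.5, "subjects must be seen as soon as possible and treated as a subject who discontinued from study treatment". Protocol 9.1.1 expects such subjects to "perform the Visit 9998/EOT (Week 104) assessments 4 weeks after their last dose" and to attend Visit 9999 twelve weeks after that. Protocol 3.6 keeps the twice-daily diary running in follow-up.

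**Data rules.** SAP 2.5.1.1 gives termination before Week 12 a hypothetical strategy. SAP 2.5.3 carries it out for stops prior to Week 12 "due to study early termination: the efficacy data collected after the discontinued treatment will be censored", followed by multiple imputation. SAP 2.14.8 applies the missing-data rules to the primary and some key secondary endpoints, then says: "All the other analyses in the final analysis will be based on the observed data". In SAP Table 2-16 the period cell for the UAS7, HSS7 and ISS7 rows is TRT1 up to Week 52. The self-administration endpoint is listed at 12 weeks after the start of self-administration, and SAP 2.6.1 counts missing values there as non-response.

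**The concern.** Keeping follow-up diary data after a stop for an adverse event or lack of efficacy fits the treatment-policy strategy the SAP has chosen. A stop imposed by the sponsor is different in kind, and the SAP recognises this up to Week 12. No visible rule carries the distinction further. A subject whose drug was withdrawn by the sponsor at, say, Week 20 could supply scores labelled Week 28, 32 and 36 of treatment. Any late-week summary of continued 120 mg pre-filled-syringe treatment would then mix in the effect of the drug being withdrawn, in the weeks that bear on durability of response.

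**Working it through.** **1. The plan's own figure.** Table 2-1 sets Week x = Day 7(x−1)+1 to Day 7x. For x = 52: 7×51+1 = 358 and 7×52 = 364, so Day 358 to 364, as the table states.

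**2. Follow-up weeks mapped to labels.** With on-schedule dosing, a last dose at Week L falls on Day 7L+1. The end-of-treatment visit (+28 days) is Day 7L+29 and the last visit (+84 days) is Day 7L+113. Labelled weeks lying wholly between the two satisfy 7(x−1)+1 ≥ 7L+29 and 7x ≤ 7L+113, so x runs from L+5 to L+16, cut at 52. *Off drug* here means these weeks.

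| Last dose, week L | End-of-treatment day | Last visit day | Off-drug weeks labelled as treatment | 4-weekly points among them |
|---|---|---|---|---|
| 4 | 57 | 141 | 9–20 | 12, 16, 20 |
| 8 | 85 | 169 | 13–24 | 16, 20, 24 |
| 20 | 169 | 253 | 25–36 | 28, 32, 36 |
| 36 | 281 | 365 | 41–52 | 44, 48, 52 |
| 40 | 309 | 393 | 45–52 | 48, 52 |
| 44 | 337 | 421 | 49–52 | 52 |
| 48 | 365 | 449 | none | none |

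**3. What the censoring reaches.** For L = 4 the Week 12 score is censored and imputed, so the primary result is safe, but nothing visible removes Weeks 13 to 20. For termination stops after Week 12 no visible censoring applies.

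**4. The self-administration endpoint.** Outside-clinic injection starts at Week 24 in the first half (Protocol 4.2), so the endpoint falls at Week 36. Week 36 is off drug when L+5 ≤ 36 ≤ L+16, that is 20 ≤ L ≤ 31; with L at least 24, these are last doses at Weeks 24 and 28. The final-analysis population in SAP 2.14.1 also counts in-clinic self-injection, which can start at Week 12. The endpoint is then Week 24, and the condition 8 ≤ L ≤ 19 with L at least 12 gives Weeks 12 and 16. If such a subject has no score at that week, SAP 2.6.1 makes the subject a non-responder.

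**5. Size, as illustration only.** Assume that a share s of subjects was still in the first half at termination, that last doses are spread evenly over the 13 dosing weeks 0, 4, …, 48, and that all complete follow-up. At week w:

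- on-drug share = (1−s) + s·P(L ≥ w−4)
- off-drug share = s·P(w−16 ≤ L < w−4)
- off-drug fraction = off-drug share ÷ (on-drug share + off-drug share)

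At w = 36 the two probabilities are 5/13 and 3/13; at w = 52 they are 1/13 and 3/13. For s = 50% at Week 52: 0.115 ÷ (0.538 + 0.115) = 0.176.

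| s | Off-drug fraction, Week 36 | Off-drug fraction, Week 52 |
|---|---|---|
| 25% | 0.064 | 0.070 |
| 50% | 0.143 | 0.176 |
| 75% | 0.243 | 0.360 |

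Take 60.5% on drug (the 72 mg figure after the third dose, Protocol 4.1.1) and assume 20% to 40% off drug. The fall is fraction × (60.5 − off-drug rate). At Week 36 it runs from 0.064 × 20.5 = 1.3 to 0.243 × 40.5 = 9.8 points; at Week 52 from 0.070 × 20.5 = 1.4 to 0.360 × 40.5 = 14.6 points.

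**The case against.** The strongest reply is that the affected outputs are mostly not visible. Apart from self-administration, every visible efficacy endpoint line in Table 2-16 is at Week 12 or between baseline and Week 12. SAP 2.5.2 runs the by-visit response summary only to Visit 204. By-visit tables to Week 52 are specified for the second planned interim, which will not be performed, and for the unplanned interim, which was added in November 2021 before the termination. Any further late-week tables, and their data rules, may sit in redacted text.

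The definitions can also be read the other way. SAP 2.1.1.2 separates the two periods. SAP 2.3.4 ends TRT1 at the later of the disposition date and the last visit numbered 201 to below 214, which would leave follow-up diary days outside TRT1. The parenthesis about follow-up in Table 2-1 may be there only so that retrieved drop-out scores can be mapped to Week 12. Finally, the hypothetical strategy belongs to the Week 12 estimand, and no estimand is stated for later weeks.

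Much of this stands, and it limits the point to what can happen as written. It does not remove it. Amendment 3 revised Table 2-16 and confined the angioedema row to Week 12, yet the UAS7 rows kept the Week 52 period. A subject stopped early never reaches Visit 214 or 301, and SAP 2.3.4 gives its end date for period duration. The self-administration endpoint falls after Week 12 on either reading.

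A reader might infer that the primary result is contaminated; the censoring and imputation in SAP 2.5.3 rule that out. A reader might also infer that the late-week use of observed data breaches a stated strategy. It does not, because that strategy was declared for Week 12 only; the gap is that the exception was not carried forward.

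**Conclusion.** The point holds as a gap in the plan, and it should be closed. As written, off-drug scores from subjects stopped by the sponsor can enter any UAS7, HSS7 or ISS7 summaries for Weeks 13 to 52 and the self-administration endpoint, and termination-related missing values count as failures in the latter.

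The likely direction is a lower late-week response. Protocol 4.2 reports partial relapse towards the end of the dosing interval at 24 and 72 mg. Against a large effect, the same section says that some subjects may not relapse for many weeks after extended treatment. Protocol 4.1 describes the 12-week follow-up as covering approximately five half-lives, so drug effect may persist in the early follow-up weeks.

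The size is not determinable. The documents give neither the number of subjects in the first half at termination nor an off-drug response rate, and the 60.5% is a 72 mg figure applied to weeks on 120 mg. The range of about 1 to 15 points is not an estimate, and a reader should not infer that a loss of that size is shown.

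**What to change.** In SAP 2.1.1.3.2 and 2.14.8, state that for stops due to study termination, diary weeks beginning after the 28 days credited to the last dose are excluded from treatment-period efficacy summaries after Week 12 and reported as FU12 weeks. The 28 days are the SAP's own exposure window (2.4.1). Count the dosing day as the first day, so that with on-schedule dosing the first excluded week is L+5. Keep follow-up diary data as retrieved drop-out data for all other stop reasons.

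For the self-administration endpoint, exclude or multiply impute termination-related missing values. Without this step, the new exclusion would turn those subjects into non-responders under SAP 2.6.1.

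Reconcile SAP 2.1.1.2, 2.1.1.3.2 and 2.3.4 on where TRT1 ends for a subject who stops early. Tables 2-2a and 2-2b need no change unless efficacy in the second treatment half is reported, since Table 2-16 shows only safety there.

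The cost is SAP wording and one derivation flag from the last-dose date and stop reason, both collected. The price is smaller denominators at late weeks: each subject stopped by termination with a last dose at Weeks 0 to 36 has 12 labelled weeks beyond the window, at Week 40 eight, at Week 44 four and at Week 48 none. Of these, only the weeks after Week 12 are removed.

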3.4 Second observation period

- Visit 301 (Week 0) to 399 (Week 52 also referred to as End of Observation Period 2, EOBS2).
- If the subject's UAS7 is ≤ 6 at Week 52, the subject will enter the second (investigational treatment-free) observation period Visit 301 (Week 0) and will be assessed remotely (i.e. outside the clinic) by a safety phone call from the site every 4 weeks, unless there is an in-clinic visit scheduled.
- Subjects will have in-clinic safety and efficacy assessments done at 12 or 16 week intervals.
- Subjects must remain on the same H1-AH background medication they were taking in the preceding studies.
- Subjects should use the same H1-AH rescue medication that was agreed with the investigator at Visit 1 of this study.
- Use of oral corticosteroid rescue medication is **not permitted** during this second observation period.

- Subjects will continue to complete the eDiary twice daily as per protocol, in order to monitor the activity of their disease. All subjects should complete their eDiary for the 7 days prior to Visit 214 (i.e. one assessment-week) to ensure the UAS7 thresholds are available.
- Subjects who present with moderate to severe active disease ($UAS7 \geq 16$) will be brought back to clinic to be treated as soon as possible to perform Visit 214 (Week 52) in the second half of the treatment period) and restart treatment with ligelizumab 120 mg PFS q4w.
- Subjects with a $UAS7 < 16$ by the end of this second observation period will perform Visit 399 (EOOBS2) of this extension study to exit the study.
- Subjects who wish to discontinue from this observation period will be expected to complete at least Visits 301, 302 and 303 (Week 0, 4 and 8), and perform Visit 399 (Week 52/EOOBS2) and exit the study.

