The strongest treatment responses across all 3 endpoints at Week 4 were seen with 72 mg and 120 mg and appeared to be comparable. Beyond Week 4, data is available for 24 mg, 72 mg and 240 mg. The response for the 72 mg and 240 mg doses appear to be similar up to Week 20. With doses of 24 or 72 mg q4w a partial relapse of symptoms towards the end of the dosing interval can be observed. These data imply that the 72 mg q4w dose achieves rapid and good control of symptoms and a dose higher than 72 mg q4w can provide enough drug exposure so that relapse of symptoms throughout the dosing interval is minimal. These data also imply that treating subjects at a monthly interval is beneficial in achieving a meaningful sustained clinical response.

During the Phase 2 study, there was no evidence of dose related safety signals up to Week 20 except for a potential trend in injection site reactions, which were mostly non-serious, mostly mild in severity, reversible and did not lead to treatment discontinuations. This observation is further supported by data from adult asthma trials where doses up to 240 mg q2w were administered. Furthermore, in the CSU Phase 2 extension study CQGE031C2201E1 which uses 240 mg q4w, no new safety signals have been observed.

[Redacted]

[Redacted]

[Redacted]

[REDACTED]

[REDACTED]

[REDACTED]

[REDACTED]

Summary

[REDACTED]

A dose of 120 mg is considered a safe dose level for this Phase 3 extension study, with a substantial safety window. To allow for retreatment efficacy comparison, a dose of 72 mg is included in this extension study until Week 12 (Visit 204). There have been no new or unexpected safety findings in the completed and ongoing studies CQGE031C2201, CQGE031C2201E1, CQGE031C2302 and CQGE031C2303 studies to date, across all the doses assessed.

Rationale for observation periods

In clinical practice, many patients with CSU require chronic treatment for their disease. In this extension study, subjects transitioning from the preceding studies who have not yet relapsed to moderate to severe disease ($UAS7 \geq 16$) will move to the first observation period of up to 36 weeks, remaining on their background and rescue H1-AH medication. Based on the Phase IIb CQGE031C2201/E1 study data, some subjects may not relapse for many weeks after

[REDACTED]

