12.4 Analysis of the primary endpoint(s)

12.4.1 Definition of primary endpoint(s)

The primary endpoint is the proportion of subjects with well-controlled urticaria at Week 12 (Visit 204) in the first half of the treatment period based on the UAS7 score. Well-controlled urticaria at Week 12 is assessed as achieving $UAS7 \leq 6$ at Week 12.

The UAS7 is the sum of the HSS7 score and the ISS7 score, and ranges from 0-42. Weekly scores (HSS7 and ISS7 scores) will be derived by adding up the average daily scores of the 7 days preceding the visit.

Regardless of the use of rescue medication or discontinuation of the study assigned-treatment due to any reason up to the assessment time point, all available data collected for UAS7 scores will be used for primary endpoint calculation.

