2.1.1.3 Study Day and Study Week

2.1.1.3.1 Study Day

Study day is defined with respect to extension and will be used for all efficacy and safety analyses. The first day of administration of study treatment (first dose) of extension study is defined as Day 1.

All other study days will be labeled relative to Day 1. For event dates on or after Day 1, study day for a particular event date will be calculated as [Date of event] - [Date of first dose] + 1. For the dates before Day 1, study day for an event date will be calculated as [Date of event] - [Date of first dose]. Hence, study days for the following critical dates are defined as follows:

- Signing ICF (Day *a*) : [Date of signing ICF] - [Date of first dose]
- Start of OBS1 (Day *b*): [Date of Visit 101] - [Date of first dose]
- Start of TRT1 (Day 1): defined as Day 1
- Start of TRT2 (Day *c*): [Date of Visit 214] - [Date of first dose] +1
- Start of OBS2 (Day *d*): [Date of Visit 301] - [Date of first dose] +1
- Start of 52-week FU (Day *e*): [Date of Visit 501] - [Date of first dose] +1

Duration of an event will be calculated as (Event end date - Event start date + 1).

The descriptor “Day 0” will not be used.

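### SAP Table 2-2b places every second-half study week for subjects who restart after the second observation period 7 days later than Table 2-2a and the weekly-score rule

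*SAP*

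**What the plan says.** The weekly score rule is the same in both documents. Protocol 12.4.1 has the weekly scores "derived by adding up the average daily scores of the 7 days preceding the visit". SAP 2.5.3 says: "The HSS7 and ISS7 score will be derived by adding up the daily HSS and ISS scores of the 7 days preceding the visit".

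SAP 2.1.1.3.2 turns study days into study weeks for the diary-based efficacy analyses, with three tables for the treatment period:

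- Table 2-1 (first half): Baseline is Days -7 to -1, Week 1 is Days 1 to 7, and Week x is Days 7(x-1)+1 to 7x.
- Table 2-2a (second half, no OBS2): Week x is Days 7(x-52)+358 to 7(x-51)+357.
- Table 2-2b (second half after OBS2): the weeks "are defined based on the study days and study day of Visit 214 (Day c) as indicated in Table 2-2b", with Week x on Days 7(x-52)+c to 7(x-51)+c-1. The first row, labelled Week 52 (V214), is Days c to c+6.

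SAP 2.1.1.3.1 defines Day c as "Date of Visit 214] - [Date of first dose] +1". For these subjects Visit 214 is the visit at which they "restart treatment with ligelizumab 120 mg PFS q4w" (Protocol 3.4).

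Table 2-4 (OBS2, start Day d) and Table 2-5 (52-week follow-up, start Day e) each give a general formula and then print a Week 52 row.

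**The concern.** The other two treatment-period tables put a visit-week label on the 7 days before the visit. Table 2-2b starts it on the visit day. The same label then means different things in the two groups of second-half subjects, and for restarting subjects it contradicts the score rule.

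The protocol gives no sign that a different convention was meant for this group. Protocol 3.4, on the second observation period, asks for complete diaries in the 7 days before Visit 214. Protocol 3.5 asks restarting subjects for the 7 days before Visit 403 (Week 64). Table 2-2b scores neither week under its visit label.

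At stake is the correct labelling of any second-half diary output for the long-term-treatment-with-a-rest subpopulation. The visible one is the eDiary rescue-tablet summary by study week (SAP 2.4.2.3.2), which SAP 2.14.3 keeps for the final analysis.

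**Working it through.** **Inputs.** Window formulas: SAP Tables 2-1, 2-2a, 2-2b, 2-3, 2-4 and 2-5. Day c: SAP 2.1.1.3.1. Nominal visit days: Protocol Table 8-1 (Visit 214 Day 365, Visit 403 Day 449, Visit 412 Day 701, Visit 9998 Day 729) and Table 8-2 (Visit 301 Day 1, Visit 399 Day 365).

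**1. Reproduce the printed rows.**

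- Table 2-2a, x=52: 7×0+358 = 358 to 7×1+357 = 364. At x=104: 7×52+358 = 722 to 7×53+357 = 728. Both as printed.
- Table 2-2b, x=52: c to 7×1+c-1 = c+6. At x=104: 7×52+c = c+364 to 7×53+c-1 = c+370. Both as printed.

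**2. Nominal visit days.** Uninterrupted subjects: Week w falls on Day 7w+1. Restarting subjects: Day c+7(w-52). For example, Visit 403 is 449-365 = 84 days after Visit 214, so it falls on Day c+84.

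**3. Compare each window with its visit.**

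| Label | Table 2-2a window | Visit day | Relative to visit | Table 2-2b window | Visit day | Relative to visit |
|---|---|---|---|---|---|---|
| Week 52 | 358 to 364 | 365 | -7 to -1 | c to c+6 | c | 0 to +6 |
| Week 64 | 442 to 448 | 449 | -7 to -1 | c+84 to c+90 | c+84 | 0 to +6 |
| Week 100 | 694 to 700 | 701 | -7 to -1 | c+336 to c+342 | c+336 | 0 to +6 |
| Week 104 | 722 to 728 | 729 | -7 to -1 | c+364 to c+370 | c+364 | 0 to +6 |

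The shift is 0-(-7) = 7 days at every label. The written window and the pre-visit window share no day. Table 2-1 agrees with Table 2-2a: Week 12 is Days 78 to 84 and Visit 204 is on Day 85.

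**4. Where the 7 days come from.** Table 2-2b is Table 2-2a with 358 replaced by c (and 357 by c-1). But 358 is the first day of the week before Visit 214, whereas c is the day of Visit 214, which corresponds to 365. Putting c=365 into Table 2-2b gives Week 52 = Days 365 to 371 and Week 104 = Days 729 to 735.

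**5. Internal logic.** Table 2-1 calls the 7 days before the first dose Baseline and starts Week 1 on the dosing day. Carried over to the restart, Days c-7 to c-1 are Week 52 and Days c to c+6 are Week 53.

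**6. Last rows of the other tables.**

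- Table 2-4, x=52: 7×51+d = d+357 to 7×52+d-1 = d+363. Printed: d+364 to d+370, which is what the formula gives for x=53.
- Table 2-5, x=52: e+357 to e+363. Printed: e+364 to e+370, the same slip.
- Table 2-3, x=36: 7×35+b = b+245 to 7×36+b-1 = b+251, as printed.

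Visit 399 falls nominally on Day d+364, and the diary is collected there from subjects not starting treatment. The printed OBS2 Week 52 window starts on that day, so it can hold at most one daily score. The rule needs four, so the weekly score would be missing. The weekly tablet total needs all seven days and would be missing too.

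**The case against.** The strongest reply is that this is a labelling slip with little reach, and on reach it is right. Table 2-2b applies only to subjects who restart after OBS2. The primary and Week 12 secondary endpoints use Table 2-1. The efficacy scope visible in SAP Table 2-16 is confined to the first half. The visible second-half outputs are otherwise safety summaries, and assessments recorded on the CRF use CRF visit weeks.

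A reader might infer more, but the documents do not support it:

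- *Bias in favour of restarted subjects because the window sits early in the dosing interval.* Protocol 4.2 does report: "With doses of 24 or 72 mg q4w a partial relapse of symptoms towards the end of the dosing interval can be observed". But second-half dosing is 120 mg, and the same paragraph takes the data to imply that relapse within the interval is minimal above 72 mg. No efficacy comparison of restarted with uninterrupted subjects is visible.
- *Every label follows a dose.* Only 13 of the 53 labels (Weeks 52, 56, ..., 100) start on a dosing day. The window includes the visit day, when the diary is completed before dosing. Week 104 has no dose.
- *A spoiled before/after monotherapy comparison.* No such analysis is visible. The site decision at Week 64 uses the 7 days before Visit 403, which Table 2-2b does not change.
- *A corrupted restart baseline.* None is defined. The efficacy baseline is the week before the first extension dose.
- *53 weeks forced into a 52-week period.* Table 2-2a also has 53 labels, as does the corrected table. The fault is the anchor.
- *An OBS2 Week 52 window that is empty or wholly after exit.* It begins on the nominal exit day. The score is missing by rule, but the window is not wholly after exit.

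One objection bears on the correction itself. Days c-7 to c-1 lie before the SAP's start of the second half (Day c) and already carry OBS2 labels. This stands and is dealt with in the fix.

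**Conclusion.** The inconsistency is real and should be corrected. For restarting subjects, all 53 labels in Table 2-2b (Weeks 52 to 104) are 7 days later than the same labels in Table 2-2a and than the 7-days-before-the-visit rule. The last rows of Tables 2-4 and 2-5 are each 7 days later than their own formulas give.

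The consequence is mislabelled weekly values in a descriptive output, not a threat to the primary or Week 12 results. No direction or size of bias is claimed.

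The conclusion assumes visits on their nominal days, and that the by-study-week rescue-tablet summary uses the study weeks of SAP 2.1.1.3. The documents do not say how many subjects restarted. Further second-half diary analyses may sit in redacted text; if so, the correction matters for those as well.

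**What to change.** 1. In Table 2-2b set Week x = Day 7(x-53)+c to 7(x-52)+c-1. This gives Week 52 = c-7 to c-1, Week 64 = c+77 to c+83 and Week 104 = c+357 to c+363. Days c to c+6 become Week 53.
2. State that Week 52 for these subjects is the pre-restart week, that it lies in OBS2, and which label each output uses for those days. Do not call it the relapse week: subjects return as soon as possible after reaching the threshold, so the qualifying week may be an earlier one.
3. Correct the last row of Table 2-4 to Days d+357 to d+363 and that of Table 2-5 to Days e+357 to e+363.
4. Rerun any second-half or OBS2 diary output already programmed from these tables.

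The cost is SAP wording and one derivation. No new data are needed.
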